3.1.2.1.5 Population-level Summary for Comparison between Treatment Conditions

The treatment effect will be the difference between AXER-204 and placebo in estimated least squares means of change from baseline in ISNCSCI Bilateral UEMS at Study Day 169 as estimated through a mixed-effects model for repeated measures (MMRM) as defined in section 8.5.2.1.

3.1.2.1.6 Sensitivity Estimand for the Primary Efficacy Objective

The robustness of the assumptions of the primary estimand will be evaluated through the use of a sensitivity estimand through the following alternative approach to intercurrent events (Table 4).

Table 4Handling of Intercurrent Events for the Sensitivity Estimand forthe Primary Efficacy Objective

Intercurrent event	Data collection and analysis
Important protocol deviation, including use of prohibited medication, prior to assessment scheduled on Study Day 169	Patients who experienced the intercurrent event will be excluded from analysis in line with a principal stratum strategy.
Did not receive at least 5 doses (~80%) of the planned cumulative number of doses of treatment	
Did not perform at least one post- baseline assessment	
Discontinuation from the study prior to assessment scheduled on Study Day 169	Patient's measurements up until the time of the intercurrent event will be used in analysis in line with the while on treatment policy, i.e. the endpoint is only evaluable in patients who complete the assessment scheduled on Study Day 169.

3.1.2.2 Estimand for 1st Secondary Efficacy Endpoint: Bilateral Prehension Performance (PP)

One of the secondary estimands is change from baseline in GRASSP Bilateral prehension performance (PP) total score to Study Day 169 between AXER-204 and placebo in patients with chronic spinal cord injury (CSCI).

The Graded Redefined Assessment of Strength Sensibility and Prehension (GRASSP V2) prehension performance sub-scale assesses performance of four tasks that mimic everyday activities of daily living. Patients are asked to 1) pour water from a bottle into a cup, 2) pull 9 pegs one-by-one out of holes on one side of a board and insert them into holes on the opposite side, 3) pick up a key, insert it into a lock and turn the key, and 4) pick up 4 nuts, one-by-one, and screw them onto matching screws. The required grasping pattern for each of the four tasks is illustrated in Figure 3.

CONFIDENTIAL

Figure 3 GRASSP Prehension Performance Illustration

Scores are assigned as follows:

- 0: The task cannot be conducted at all
- 1: The task cannot be completed, (less than 50% of the task)
- 2: The task is not completed, (50% or more of the task)
- 3: The task is conducted (completed) using tenodesis or an alternative grasp other than the expected grasp.
- 4: The task is conducted using the expected grasp with difficulty (lack of smooth movement or difficult slow movement)
- 5: The task is conducted without difficulties using the expected grasping pattern and unaffected hand function

Each task must be completed within 75 seconds and the number of drops is recorded. Each side is tested and the scores combined to obtain the bilateral score.

There is a substantial concurrence between GRASSP prehension performance and activities of daily living from a patient perspective (Kalsi-Ryan et al. 2019).

Accordingly, GRASSP prehension performance provides an objective, clinicianevaluated measure of function in performing activities of daily living.

3.1.2.2.1 Treatment Condition of Interest

The treatment condition of interest is the same as section 3.1.2.1.1.

3.1.2.2.2 Population

The population is the same as section 3.1.2.1.2.

3.1.2.2.3 Endpoint

The endpoint is the change from baseline in GRASSP Bilateral prehension performance (PP) score to Study Day 169.

3.1.2.2.4 Handling of Intercurrent Events

The intercurrent events strategy is the same as section 3.1.2.1.4.

3.1.2.2.5 Population-level Summary for Comparison between Treatment Conditions

The treatment effect is the same as section 3.1.2.1.5, except the endpoint is as described in section 3.1.2.2.3.

3.1.2.2.6 Sensitivity Estimand for the 1st Secondary Efficacy Objective

The sensitivity estimand is the same as section 3.1.2.1.6.

3.1.2.3 Estimand for 2nd Secondary Efficacy Endpoint: SCIM III Self Care

One of the secondary estimands is change from baseline in SCIM III Self Care score to Study Day 169 between AXER-204 and placebo in patients with chronic spinal cord injury (CSCI).

The Spinal Cord Independence Measure, Version III (SCIM III) questionnaire has been widely used to assess performance of activities of daily living. It relies on patient responses to 17 questions across three domains: self-care, respiration and sphincter management, and mobility. This study is collecting data for self-care and mobility and self-care has been selected as a secondary efficacy measure based on the expectation that the change in this domain will be most reflective of changes in arm and hand function being measured with the primary efficacy measure of change in ISNCSCI UEMS.

The self-care sub-scale is comprised of four questions to determine the level of independence in feeding, bathing (upper body, lower body), dressing (upper body, lower body), and grooming with a possible score of 0-20 points.

The SCIM III minimal clinically important difference has not been determined for patients with chronic SCI.

3.1.2.3.1 Treatment Condition of Interest

The treatment condition of interest is the same as section 3.1.2.1.1.

CONFIDENTIAL

3.1.2.3.2 Population

The population is the same as section 3.1.2.1.2.

3.1.2.3.3 Endpoint for the Secondary Estimand

The endpoint is the change from baseline in SCIM III Self Care score to Study Day 169.

3.1.2.3.4 Handling of Intercurrent Events

The intercurrent events strategy is the same as section 3.1.2.1.4.

3.1.2.3.5 Population-level Summary for Comparison between Treatment Conditions

The treatment effect is the same as section 3.1.2.1.5, except the endpoint is as described in section 3.1.2.3.3.

3.1.2.3.6 Sensitivity Estimand for the 2nd Secondary Efficacy Objective

The sensitivity estimand is the same as section 3.1.2.1.6.

3.1.2.4 Estimand for 3rd Secondary Efficacy Endpoint: Patient Global Impression of Change (PGIC)

One of the secondary estimands is Patient Global Impression of Change (PGIC) responder rate at Study Day 169 between AXER-204 and placebo in patients with chronic spinal cord injury (CSCI).

The PGIC instrument captures the patient's overall evaluation of response to treatment. Specifically, the PGIC asks: "Since beginning this clinical trial, how would you describe the overall change (if any) related to your chronic spinal cord injury?" The patient is asked to report the degree to which they have changed since entering the treatment period using a 7-point Likert scale (1= 'Much worse', 2='Worse', 3=' A little worse', 4='No change', 5='A little better', 6='Better, 7=''Much better') and "If better or worse, what has changed?". Patients that have evaluation results including "Much better", "Better", or "A little better" at Study Day 169 are considered Responders. This provides a global assessment from the patient's perspective and may capture anticipated and unanticipated changes that occur during the study.

Overall, these scales administered by trained raters in this double blinded, placebocontrolled study will provide a reliable assessment of treatment-related changes from baseline in upper extremity motor function, including performance of activities of daily living, and capture any changes related to the patient's own assessment of their chronic SCI.

CONFIDENTIAL

Document	Date:	05	August	2022
Document	Date.	05	August	2022

Rater Training: Given the importance of these measures to assess functional changes, activities of daily living and clinical relevance, ReNetX established a comprehensive training for raters across all measures including certification directly from the groups that developed and standardized these measures.

3.1.2.4.1 Treatment Condition of Interest

The treatment condition of interest is the same as section 3.1.2.1.1.

3.1.2.4.2 Population

Sponsor Protocol ID: RNX-AX204-101

The population is the same as section 3.1.2.1.2.

3.1.2.4.3 Endpoint

The endpoint is the Patient Global Impression of Change (PGIC) responder rate at Study Day 169. Patients that have evaluation results including "Much better", "Better", or "A little better" are considered Responders, whereas patients that have evaluation results including "Much worse", "Worse", "A little worse", or "No change" are considered Non-Responders.

3.1.2.4.4 Handling of Intercurrent Events

The intercurrent events strategy is the same as section 3.1.2.1.4.

3.1.2.4.5 Population-level Summary for Comparison between Treatment Conditions

The treatment effect will be the difference between AXER-204 and placebo in percentages of PGIC responder rate at Study Day 169 as estimated through a Fisher's Exact Test as defined in section 8.5.2.2.

3.1.2.4.6 Sensitivity Estimands for the 3rd Secondary Efficacy Objective

The first sensitivity estimand is the same as section 3.1.2.1.6. Another sensitivity estimand will follow an alternative approach to intercurrent events (Table 5).

Table 5Handling of Intercurrent Events for the Sensitivity Estimand for
the 3rd Secondary Efficacy Objective

Intercurrent event	Data collection and analysis	
Important protocol deviation, including use of prohibited medication, prior to assessment scheduled on Study Day 169	Patients will be followed and data collected after the intercurrent event will be used in analysis in line with the treatment policy strategy, i.e. regardless of the intercurrent event.	
Did not receive at least 5 doses (~80%) of the planned cumulative number of doses of treatment		
Did not perform at least one post- baseline assessment	Patients who experienced the intercurrent event will be excluded from analysis in line with a principal stratum strategy.	
Discontinuation from the study prior to assessment scheduled on Study Day 169	Among patients who experienced the intercurrent event, the intercurrent event will be integrated in the response variable in line with the composite variable strategy, i.e. considered to be Non-Responder (4='No change').	

3.1.2.5 Exploratory Efficacy Endpoints

3.1.2.5.1 Change from baseline to Study Day 169

- ISNCSCI Unilateral UEMS of the side with higher baseline scores ranging from 0-25. For each patient, choose the side with higher baseline unilateral UEMS score and all post-baseline value and change from baseline values for the same side will be analyzed. If the baseline scores for each side are equal, then the right side will be grouped with the higher baseline UEMS scores for analysis.
- ISNCSCI Unilateral UEMS of the side with lower baseline scores ranging from 0-25. If the baseline scores for each side are equal, then the left side will be grouped with the lower baseline UEMS scores for analysis. The analysis will be similar to the one with higher baseline UEMS scores as described above.
- ISNCSCI Bilateral Motor score (including both upper and lower extremity for both left and right sides) with scores ranging from 0-100.
- ISNCSCI Bilateral Sensory score light touch (sum of right total and left total) with scores ranging from 0-112.

- ISNCSCI Bilateral Sensory score pin prick (sum of right total and left total) with scores ranging from 0-112.
- GRASSP Bilateral Strength score (sum of score from left and right) with scores ranging from 0-100.
- GRASSP Bilateral Sensation total score (sum of score from left and right) with scores ranging from 0-24.
- GRASSP Bilateral Prehension Ability (PA) total scores (sum of score from left and right) with scores ranging from 0-24.
- $_{\odot}~$ SCIM III mobility score (see section 3.1.1 for details) with scores ranging from 0-40.
- CUE Questionnaire (CUE-Q) total score with scores ranging from 0-128.
 CUE-Q contain 17 questions each on a scale of 0 to 4 to assess subject reported upper limb function for both arms or hands including Ability to reach or lift, Ability to pull and push with arms, Moving and positioning arm and wrist, and Using hands and fingers.
- Neuro-QoL upper extremity function t-score, with overall raw score ranging from 20-100. Neuro-QoL upper extremity function questionnaire consist 20 questions to assess upper extremity function (fine motor or ADL). All questions are rated on a 1- to 5-point verbal rating scale with higher score associated with better function.
- SF-36 score. SF-36 V2 provides a patient-reported QoL assessment on subjects' perceived health and well-being over the course of the study. The following derived scales will be determined (Optum PRO CoRE):
 - Bodily Pain
 - General Health
 - Mental Health
 - Mental Component
 - Physical Component
 - Physical Functioning
 - Social Functioning
 - Role Emotional
 - Role Physical
 - Vitality
 - SF-6D (Utility Index)
 - SF-6D_R2 (Utility Index Release 2)

3.1.2.5.2 Other exploratory efficacy endpoints

- ISNCSCI ASIA impairment scale (AIS) with scales including A, B, C, D, E (protocol Appendix 3) at Study Day 169.
- ISNCSCI Neurological Motor level at Study Day 169.
- ISNCSCI Neurological Sensory level at Study Day 169.
- ISNCSCI Neurological Level of Injury (NLI) at Study Day 169.
- ISAFSCI assessments at Study Day 169. The ISAFSCI documents autonomic control of the heart, blood pressure, sweating and temperature regulation with findings equal to one of the following values: Normal, Abnormal, Unknown, or Unable to assess. Scores for lower urinary tract, bowel or sexual function will also be collected whereas score 0= complete loss of control; 1= Reduced or Altered Neurological Function; 2 = Normal function; NT=Unable to assess.
- Clinical Global Impression of Change (CGIC) from GRASSP Prehension Performance Video Recordings. Details are included below as this measure has been added beyond specific information included in the protocol. Conducted by a blinded rater who is trained on the scales and also has a C5/C6 injury to provide the perspective of the patient population we intend to treat with our therapy: Given the importance of this measure for functional, ADL as well as patient/clinically relevant changes, the GRASSP prehension performance assessment is video recorded at each time point to visually document changes reflected in the scoring as well as changes that may or may not be captured on the scale.

CGIC Evaluation

Compared to baseline, how would you describe the overall change (if any) related to performance of the GRASSP prehension performance tasks?

Choose ONE.

- ____Much worse (1)
- _____Worse (2)
- _____A little worse (3)
- ____No change (4)
- _____A little better (5)
- _____Better (6)
 - ___Much better (7)

If better or worse, what has changed? _

With the exception of the CGIC, all efficacy endpoints will also be analyzed for Study Day 253.

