## **13.** ASSESSMENT OF EFFICACY AND PHARMACOKINETICS

#### 13.1. Efficacy

Site personnel will be trained and certified to perform the efficacy assessments. The same raters will be used for evaluation of a given subject insofar as possible. Raters will be blinded to treatment for Part 2 of the trial.

#### 13.1.1. Part 1

Part 1 is focused on safety, tolerability, and pharmacokinetics. However, a subset of efficacy assessments are included, as follows:

- ISNCSCI. ISNCSCI is a comprehensive clinician-administered neurological exam for SCI. It is widely used for research and clinical (neurologic) description to fully assess sensory and motor functioning and level of injury in traumatic SCI. The UEMS will be calculated from the full ISNCSCI and evaluated separately.
- GRASSP [Kalsi-Ryan 2012a, Kalsi-Ryan 2012b]. GRASSP is a clinician administered test with three subset scores that assesses strength in 10 key muscles in the upper extremity as well as dexterity and fine motor skills.
- SCIM III self-care and mobility scores [Catz 2007, Itzkovich 2007]. SCIM III measures functional outcomes in three sections: self-care, respiration and sphincter management, and mobility. The current study will employ the self-care and mobility subscores.

#### 13.1.2. Part 2

The primary objective of Part 2 is to evaluate the safety, tolerability, and pharmacokinetics of repeat dosing. In addition, a number of efficacy assessments are included as secondary endpoints. The key secondary efficacy endpoint for Part 2 will be within-subject change from pre-treatment baseline and slope for UEMS as compared to placebo. The UEMS is collected as part of the ISNCSCI (Appendix 3).

Additional secondary efficacy endpoints will include changes from pre-treatment baseline and slope for:

- Graded Redefined Assessment of Strength, Sensation and Prehension (GRASSP) prehension performance scores. GRASSP is a clinician administered test with three subset scores that assesses strength in 10 key muscles in the upper extremity as well as dexterity and fine motor skills (Appendix 4).
- Version III of the Spinal Cord Independence Measure (SCIM III) self-care. SCIM III measures functional outcomes in three sections: self-care, respiration and sphincter management, and mobility. The current study will employ the self-care and mobility subscores. The evaluation will be administered by a clinician (Appendix 8).

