8.5.2.3 Exploratory Efficacy Endpoints

For exploratory efficacy endpoints of changes from baseline in assessment results (as listed in section 3.1.2.5.1), analysis will be conducted using the same methodology as that used for the primary efficacy endpoint (sections $\underline{8.5.2.1}$ and $\underline{8.5.2.1.1}$).

For other exploratory efficacy endpoints at Study Day 169:

- ISNCSCI ASIA impairment scale (A, B, C, D, E) will be summarized descriptively as the number and percent of subjects with each response at each visit by treatment group.
- ISNCSCI Neurological Motor level will be summarized descriptively as the number and percent of subjects by body part by treatment group.
- ISNCSCI Neurological Sensory level will be summarized descriptively as the number and percent of subjects by body part by treatment group.
- ISNCSCI Neurological Level of Injury (NLI) will be summarized descriptively as the number and percent of subjects by body part by treatment group.
- ISAFSCI assessments: for each system/organ, shift table of baseline evaluation to Study Day 169 evaluation will be created.
- Clinical Global Impression of Change (CGIC) from GRASSP Prehension Performance Video Recordings. Assessments of Baseline compared to Day 169 will be completed and scores will be assigned using the 7-point Likert scale questions shown below and the Fisher's exact test at two-sided significance level 0.05 will be used to test if there is a difference in ratings (1= 'Much worse', 2='Worse', 3=' A little worse', 4='No change', 5='A little better', 6='Better, 7=''Much better') at Study Day 169 between patients in treatment group and control group. In addition, the Fisher's exact test will be used to compare responder rate (proportion of patient in mITT Analysis set with responses of 'A little better', 'Better', or 'Much better') at Study Day 169 between the two treatment groups. A descriptive table summarizing number and percentage of patients for each of the seven above responses by visit and treatment group will be created.

All efficacy endpoints will also be analyzed for Study Day 253 similar to the analysis conducted for Study Day 169 for each corresponding endpoint. All post treatment values up until Study Day 253 will be included in the analysis of treatment effect for Study Day 253.

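### The CGIC video rating needs the rater to know which clip is baseline, so expectation of improvement can inflate responder percentages in both arms; its effect on power is uncertain, and masking clip order is a cheap safeguard

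*SAP*

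**What the plan says.** SAP 3.1.2.5.2 introduces the CGIC as an addition to the protocol and gives its details there. The recordings exist for every assessment: "the GRASSP prehension performance assessment is video recorded at each time point". The rating is "Conducted by a blinded rater who is trained on the scales and also has a C5/C6 injury"; what the rater is blinded to is not stated. The form's question is "Compared to baseline, how would you describe the overall change (if any) related to performance of the GRASSP prehension performance tasks", answered on seven points from much worse (1) through no change (4) to much better (7).

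SAP 8.5.2.3 fixes the pair and its direction: "Assessments of Baseline compared to Day 169 will be completed and scores will be assigned using the 7-point Likert scale questions shown below". It plans two comparisons at Day 169. For the seven categories, "Fisher's exact test at two-sided significance level 0.05 will be used to test if there is a difference in ratings". For responders, meaning scores 5, 6 or 7, a second Fisher's exact "test will be used to compare responder rate".

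Protocol 13.1 says what rater blinding means for the site assessments: "Raters will be blinded to treatment for Part 2 of the trial". I found nothing in either document on masking the visit, randomising the order of clips, or re-signing scores after a masked comparison.

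**The concern.** Blinding to treatment is not blinding to time. A rater who has to score Day 169 against a known baseline knows which clip was taken after dosing, and may lean towards seeing improvement in it. The responder cut-off is the mildest category of improvement, so a lean of one step from 'no change' reclassifies a subject. The SAP describes one rater and plans no second reader to offset one person's expectation.

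Two things are at stake. The first is the responder percentages themselves, which would be too high in both arms. The second is the arm comparison: if unimproved subjects in both arms are turned into responders, the difference shrinks. Stored video is the one setting in this trial where time could be masked at almost no cost, and the plan does not use that advantage.

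**Working it through.** **1. Does the rater have to know the order?** The 3.1.2.5.2 form asks for change from baseline, and 8.5.2.3 names the pair as baseline and Day 169. The answer has a direction (better or worse), so it cannot be given without knowing which clip is which. That the rater knows the order is therefore an inference from the form. How clips are presented is never described.

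**2. Inputs.** From the documents: two-sided Fisher's exact test at 0.05; about 32 subjects randomised 1:1, so 16 per arm; responder = score 5 or more. The plan gives no CGIC responder rate or power, so there is no figure of its own to reproduce. Assumed: the true responder rates, the size of the expectation effect, and its form. Power is exact, by enumerating all outcomes with 16 per arm.

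**3. Model 1: a fraction f of unimproved subjects in each arm is rated better.**

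Observed rate = p + f(1 − p), so observed difference = (1 − f) × true difference.

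For 10% v 50% and f = 0.2:
- placebo: 0.10 + 0.2 × 0.90 = 0.28
- AXER-204: 0.50 + 0.2 × 0.50 = 0.60
- difference: 0.32 = 0.8 × 0.40

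| True rates | f = 0 | f = 0.1 | f = 0.2 | f = 0.3 |
|---|---|---|---|---|
| 10% v 50% | 58% | 41% | 31% | 23% |
| 10% v 60% | 79% | 63% | 50% | 38% |
| 20% v 60% | 51% | 40% | 31% | 23% |

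Dilution is built into this model, because only unimproved subjects can be misrated.

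**4. Model 2: the same upward shift s (in SD) in both arms on a probit scale.**

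Observed rate = Φ(Φ⁻¹(p) + s). For 10% v 50% and s = 0.5 this gives 22% v 69%, a difference of 47 points rather than 40.

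| True rates | s = 0 | s = 0.25 | s = 0.5 | s = 1 | s = 1.5 |
|---|---|---|---|---|---|
| 10% v 50% | 58% | 64% | 68% | 65% | 52% |
| 10% v 60% | 79% | 83% | 85% | 79% | 65% |
| 20% v 60% | 51% | 54% | 52% | 42% | 23% |

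Power rises for moderate shifts and falls for large ones. The turning point depends on the true rates.

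**5. What holds under both models.** The responder percentages rise in both arms. In the 10% v 50% case, f = 0.2 gives 28% v 60%, and s = 0.5 gives 22% v 69%.

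**6. What masking order recovers.** Under Model 1 with f = 0.2, suppose the same total error remains but splits evenly between better and worse. Then only f/2 = 0.1 counts upwards:
- placebo: 0.10 + 0.1 × 0.90 = 0.19
- AXER-204: 0.50 + 0.1 × 0.50 = 0.55
- difference: 36 points; power 41%

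The gain is from 31% to 41%, not back to 58%.

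**The case against.** The strongest reply is that a lean shared by both arms does no clear harm to the comparison. The rater is blinded, so the lean should be the same in each arm and cannot create a treatment effect. Whether it costs power depends on the error model, and Model 2 shows power can rise. Both points stand. A reader might infer that known order necessarily dilutes the difference, or that it undermines the validity of the test. The documents and the arithmetic support neither.

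The documents also give no evidence that raters score later clips higher, and they do not say in so many words that the rater is told the order. The Protocol 13.1 statement on blinding concerns trained site personnel, so it does not settle the scope of blinding for this separate video rater. These points are fair. They leave a bias that is plausible and unguarded, but not demonstrated.

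The endpoint also carries little weight. It is exploratory, and 3.1.2.5.2 exempts it from the Day 253 analysis. Patient-perceived change is covered by PGIC, and the same tasks are scored on GRASSP prehension performance; both are secondary endpoints.

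Finally, SAP section 10 was written after unblinding and after the Day 169 top-line analysis, which covered exploratory endpoints. The CGIC has probably been rated already, so a re-read would be post hoc, and the same rater would have seen the clips before.

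What survives is the inflation of the responder percentages, which appears under both models, and the absence of any stated masking procedure.

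**Conclusion.** The point holds as a minor one. As printed, the form requires a rater who knows which clip is baseline, and no masking of order is planned. Expectation can therefore raise the percentage rated at least 'a little better' in both arms, so those percentages should not be read as absolute rates of visible improvement.

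A loss of power is possible but not established. At assumed rates of 10% v 50% with 16 per arm, it runs from 58% to 31% if 20% of unimproved subjects are misrated. An equal latent shift instead gives 68% at 0.5 SD and 52% at 1.5 SD. All rates, the size of the effect and its form are assumptions. Type I error is not affected while the rater stays blinded to arm. A reader might also infer that random order would restore the full power; it removes the direction of the error, not the error itself.

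**What to change.** Present each subject's baseline and Day 169 recordings as clips A and B in random order, with dates and visit labels removed. Reword the question neutrally to ask for change in B relative to A on the same seven points. Someone other than the rater holds the order key and, for reversed pairs, replaces the score by 8 minus the score before analysis. The scale is symmetric about 4, so the reversal is exact. State in SAP 3.1.2.5.2 what the rater is blinded to.

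The cost is an order key and masked file names; no new patient data are needed.

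If ratings were made with the order known, say so in the report and caveat the responder percentages. Then re-read the roughly 32 pairs under masking, as a sensitivity analysis labelled post hoc. If the same rater does the re-read, note that the clips had been seen before.
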